
Study design
	
This is a multicenter, Phase 2 study to assess the activity of tesevatinib in subjects with NSCLC and activating EGFR mutations and BM or LM.
 
Screening and Study Treatment
 
After completion of the screening assessments and confirmation of study eligibility, tesevatinib will be orally administered to all subjects at a dose of 300 mg once daily. Tumor response, both in the CNS and outside the CNS, will be assessed after the second cycle of treatment and then at the end of every two cycles of treatment thereafter. Subjects will usually receive treatment with tesevatinib only until disease progression occurs, however treatment beyond progression is permissible in certain circumstances (See Duration of Treatment).
 
Measuring response in LM is complex.¹⁰ Subjects with LM entering the study will be required to have MRI evidence of LM or cytological evidence of LM or both. Thus in subjects with LM, response will be measured by symptom improvement, disappearance of signs of LM on MRI and/or by improvement in cytological results.
 
Subjects will undergo safety evaluations, including physical examination, vital sign measurements, hematology, serum chemistry, urinalysis and ECG. MRI/computed tomography (CT) will be performed to evaluate peripheral tumor lesions. MRI will be performed to evaluate both BM and LM tumor involvement. For subjects with LM in Cohort B, lumbar puncture (LP) will be performed to evaluate CSF levels of tesevatinib, CSF malignant cell numbers by standard cytology and by rare cell capture techniques, CSF cell-free DNA, and detection of activating EGFR mutations in CSF cell-free DNA.
 
End of Treatment Visit
 
An End-of-Treatment visit is to occur within 3 days after the subject's last dose of study drug. This may occur at the visit at which disease progression is diagnosed. The subject will continue to be followed in the study for disease progression and survival.
 
Follow-Up Period
 
A follow-up visit will occur 30 days (±5 days) after the last dose of study drug. Subjects will undergo PEs; vital sign measurements; hematology, serum chemistry, and urinalysis, all performed prior to the start of any new therapy. This visit may occur prior to 30 days if a new therapy is started within 30 days of last dose of study drug.
 
Long-Term Follow-Up

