	After withdrawal from the active treatment portion of the study, subjects will be contacted by telephone every 8 weeks to assess survival status and any subsequent anti-cancer treatment.
Study population/Number of subjects	Up to 20 subjects with NSCLC who have progressed with BM will be enrolled in Cohort A. Up to 20 subjects who have initial presentation or progressed with LM will be enrolled in Cohort B. Up to 20 subjects with NSCLC and BM and no prior systemic therapy will be enrolled in Cohort C. Cohort A, Cohort B, and Cohort C will be open for enrollment simultaneously; when one cohort has completed enrollment the other cohorts will remain open for enrollment until enrollment in those cohorts are also complete.

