- c: Safety labs = hematology and clinical chemistry and urinalysis. Note that Cycle 1 Day 1 labs need not be repeated if screening visit occurred within 4 days prior to Day 1 visit. Safety labs will also be done at C2D15, C3D15, C4D15, C5D15, and C6D15; they are to be done locally and will include serum chemistry only. There will be a 3 day window for the D15 chemistry labs. Cystatin C does not need to be included in the chemistry labs done on C2D15, C3D15, C4D15, C5D15, and C6D15.
 - d: Pregnancy tests will be done using urine samples in women of childbearing potential. Subject must have a negative urine pregnancy test documented within the 24-hour period prior to the first dose of study drug. Confirm with serum testing if urine sample is positive..
 - e: Supine 12-Lead ECGs will be performed at screening; Days 1, 7 and 14 of Cycle 1; on Day 1 of Cycles 2 and Day 1 of each Cycle including at End of Study Drug Treatment visit Assessment to be performed at predose, and once within 4 – 8 hours postdose for Days 1, 7 and 14 of Cycle 1. At each timepoint, repeat ECG three times consecutively within 30 minutes (must have an interval of at least 1–2 minutes between ECGs).
 - f: Tumor assessment is to be performed at screening, at C2D1, on C3D1, and after every 2 cycles (beginning on Day 1 of Cycle 3 [\pm 7 days]). Tumor assessment should include brain MRI. Peripheral (non-CNS) tumor may be assessed with either CT or MRI, but method of assessment should be the same throughout the study. Tumor assessment on C2D1 will be limited to brain MRI.
 - g: Bone scans are to be performed at screening and then as clinically indicated.
 - h: Tesevatinib will be administered at the dose of 300 mg once daily.
 - i: EORTC QLQ-C30 and EORTC QLQ-BN20 questionnaires administered at screening, on Day 1 of Cycle 3, and on Day 1 of odd-numbered cycles thereafter and EOS
 - j: AEs are to be collected from the time of informed consent through 30 days after last dose of study drug.
 - k: The End-of-Study Drug Treatment visit is to occur within 3 days after the subject's last dose of study drug. This may occur at the visit at which disease progression is diagnosed. Tumor assessment does not need to be performed if it was performed in the previous 8 weeks.

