9.2.10 End-of-Study Drug Treatment Visit

Subjects are to return to the study site within 3 days after the subject's last dose of study drug to complete all end-of-study drug treatment assessments as described below. This may occur at the visit at which disease progression is diagnosed.

- Complete physical examination, including weight
- Vital sign measurements (sitting blood pressure, pulse, respiratory rate, temperature)
- ECOG Performance status

-
- Leptomeningeal metastasis symptom assessment – Cohort B only.
 - Hematology, serum chemistry, and urinalysis
 - Urine pregnancy test, if applicable (positive results to be confirmed by serum pregnancy testing)
 - Supine 12-Lead ECG (repeat three times consecutively within 30 minutes [must have an interval of at least 1-2 minutes between ECGs])
 - Tumor assessment (brain MRI, thoracic and abdominal CT/MRI) (only required if one hasn't been performed in the previous 8 weeks)
 - Quality of Life Questionnaire
 - Concomitant medications
 - AE assessment
 - Final return and accounting of study drug

9.2.11 30-Day Follow-Up

The 30-Day Follow-Up should occur 30 days (\pm 5 days) after the subjects' last dose of tesevatinib, but prior to starting new therapy. This may occur prior to 30 days if new therapy is started within 30 days of last dose of study drug.

- Complete physical examination, including weight
- Vital sign measurements (sitting blood pressure, pulse, respiratory rate, temperature)
- ECOG Performance status
- Hematology, serum chemistry, and urinalysis
- Urine pregnancy test, if applicable (positive results to be confirmed by serum pregnancy testing)
- Concomitant medications
- AE assessment

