9.2.12 Follow-Up Phone Contact

Beginning 8 weeks after the 30-Day Follow-Up Visit, subjects are to be contacted by telephone every 8 weeks to assess survival status and any subsequent anti-cancer treatment.

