11.1.1 Tesevatinib Administration

Tesevatinib will be administered at the dose of 300 mg once daily. One cycle will be defined as 28 days of treatment.

Study drug may be taken with or without food at approximately the same time every morning (unless there is a patient-specific rationale to take it regularly at a different time of day). Subjects should drink a full glass of water (approximately 8 ounces [240 mL]) immediately after study drug administration. Grapefruit and similar (pomelo fruit, Seville oranges, etc.) products should be avoided for the duration of study treatment.

Subjects must be instructed not to make up missed doses unless the missed dose can be taken within 12 hours of the normal dosing time. Subjects should not re-take study drug doses in the event of vomiting.

Subjects will be treated with study drug until disease progression or unacceptable toxicity occurs. However, subjects with limited peripheral disease progression (oligoprogressive disease) may receive local ablative (radiation therapy or surgery) and then be continued on tesevatinib. Subjects who discontinue tesevatinib treatment will be followed for survival. (Both CNS and non-CNS disease progression are defined in Appendices A and B.)

All subjects also will be followed for a period of 30 days following their last dose of tesevatinib. Additionally, subjects will be contacted every 8 weeks to collect information on survival and other therapies.

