14 EFFICACY

In addition to bone scan at screening, CT scans of the thorax and abdomen will be performed at screening, after Cycle 2, and then every two cycles thereafter until disease progression.

Radiological disease assessments by brain MRI will be performed at screening, at C2D1, at C3D1, and then every two cycles until disease progression. Response for peripheral disease and for BM will be evaluated according to RECIST, Version 1.1. Response will be recorded separately for non-CNS disease, for BM, and for LM. All CT and MRI scans will be collected for central review. All clinical decisions during the study will be based on local site radiology assessments, which will also be used for the primary efficacy analysis.

For subjects with BM (Cohort A and Cohort C) efficacy will be evaluated by RECIST 1.1 criteria separately for non-CNS tumor lesions and for BMs at Screening, at Cycle 2 Day 1 (for BM), at Cycle 3, and then every 2 cycles (approximately 8 weeks) thereafter until disease progression.

For subjects with LM (Cohort B), symptoms attributed to leptomeningeal disease will be evaluated at screening, Cycle 1 Day 1, at Cycle 1 Day 14, at Cycle 2 Day 1, at Cycle 3, and then every 2 cycles (approximately 8 weeks) thereafter until disease progression.

The response efficacy endpoints will be evaluated separately for peripheral disease, for BM, and for LM, and a summary response will also be derived (See Table 14-1). For LM, if positive CSF cytology and MRI diagnostic findings were both present at screening, complete response (CR) requires the absence of LM by both modalities. For LM, CR also requires the complete resolution of symptoms and signs attributed to LM. Best overall response, duration of response, and duration of stable disease will be reported, based on the examples in Table 14-1. The median PFS, rate of CNS non-progression at 3 and 6 months, non-CNS time to progression, CNS TTP, and median OS also will be assessed.

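### Follow-up for progression after stopping drug is promised but not scheduled, and most end-of-treatment scans are waived, so progression may go unobserved in subjects who stop without PD

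*Protocol*

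**What the plan says.** **After treatment.** The Protocol synopsis, under End of Treatment Visit, says "The subject will continue to be followed in the study for disease progression and survival". Under Long-Term Follow-Up it says only that "subjects will be contacted by telephone every 8 weeks to assess survival status and any subsequent anti-cancer treatment", and Section 9.2.12 repeats this. Section 11.1.1 says "Subjects who discontinue tesevatinib treatment will be followed for survival", as do the synopsis and SAP Section 1.2.4. The 30-day visit (Section 9.2.11) lists examination, vital signs, ECOG, laboratory tests, pregnancy test, concomitant medication and adverse events. It has no imaging and no LM symptom assessment. Tables 4-1 and 4-2 mark no tumor assessment in the 30-day or long-term columns.

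**The end-of-treatment scan.** Footnote k of Table 4-1 and footnote n of Table 4-2 say: "Tumor assessment does not need to be performed if it was performed in the previous 8 weeks". Section 9.2.10 lists brain MRI with thoracic and abdominal imaging and adds "only required if one hasn't been performed in the previous 8 weeks".

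**On treatment.** Section 14 sets assessments for Cohorts A and C "at Cycle 3, and then every 2 cycles (approximately 8 weeks) thereafter until disease progression". Footnote f of both tables adds: "Tumor assessment on C2D1 will be limited to brain MRI".

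**Analysis.** Appendix A defines PFS as time from start of therapy to documented progression or death. SAP Section 2 and its Table 1 plan descriptive summaries and Kaplan-Meier curves for PFS, OS, CNS TTP and non-CNS TTP. Neither document states a censoring rule.

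**The concern.** Section 10.1.1 allows treatment to stop for adverse events, withdrawal or noncompliance as well as for progression. For a subject who stops without PD, the end-of-treatment visit is the last scheduled occasion at which progression could be found, and the scan at that visit is usually waived. After it, the schedule captures death and new therapy but not progression.

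At stake are secondary objectives of all three cohorts: PFS, CNS TTP, non-CNS TTP and the CNS non-progression rates at 3 and 6 months. If subjects who stop early tend to progress sooner than those who stay on drug, losing their progression dates makes these results look better than they are. The SAP does not say how such subjects are to be handled, so the analyst would have to choose once the data are known.

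**Working it through.** The documents contain no figure for stopping without PD. Their one probability statement, the sample-size justification, reproduces (exact binomial, n = 20, rate 20%: at least 3 responders 79.4%, at least 2 responders 93.1%) but does not bear on this point.

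**Step 1. What can find progression after the last dose.**

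| Contact | Imaging | Progression asked |
|---|---|---|
| End-of-treatment visit, within 3 days of last dose | Waived if done in previous 8 weeks | LM symptoms assessed (Cohort B), not waived |
| 30-day visit | None | No |
| Telephone, every 8 weeks | None | No; survival and later therapy only |

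**Step 2. Waiver against scan interval.** Cycles are 28 days. Brain MRI falls on Day 29; full assessments fall on Days 57, 113, 169 and so on. The longest regular gap is 113 − 57 = 56 days = 8 weeks, exactly the waiver window.

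I simulated 200,000 stops per setting. Screening scans fell 1 to 28 days before Day 1, later scans were on time or within ±3 or ±7 days, and the visit came 0 to 3 days after the last dose. The waiver was applied separately to brain and body. The stopping-time distributions are my assumptions.

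| Stopping time | Last brain MRI ≤ 56 days old | Last body scan ≤ 56 days old |
|---|---|---|
| Even over Days 1–336 | 96–99% | 91–94% |
| Exponential, median 60 to 180 days | 98–99% | 88–93% |
| Subset of the first row: from Day 57 | 95–99% | 95–99% |
| Subset of the first row: before Day 57 | over 99% | 72–75% |

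**Step 3. Stops before Cycle 3 Day 1.** Take an end-of-treatment visit on Day 49 and a screening body scan d days before Day 1. Its age is 48 + d days, which is at most 56 only if d ≤ 8. If the waiver is read by compartment, a body scan is still required for d = 9 to 28. That is 20 of 28 days, or 71% if screening dates are uniform. If instead the Day 29 brain MRI (49 − 29 = 20 days old) counts as the tumor assessment, the body scan is waived and the subject leaves with no post-baseline thoracic or abdominal scan. The footnotes leave this open.

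**Step 4. Possible size.** I compared Kaplan-Meier estimates with scans continued to PD against censoring at the last scan before stopping (40,000 simulated subjects per scenario, brain-scan calendar, end-of-treatment scan always waived, no deaths). Progression medians, stopping rates and hazard ratios after stopping are all assumptions. Selected rows, non-progression in percent (continued / censored):

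| Progression median | Stopped without documented PD | Hazard after stopping | 3 months (Day 91) | 6 months (Day 183) |
|---|---|---|---|---|
| 84 days | 36% | 1× | 63.0 / 63.1 | 24.9 / 25.0 |
| 84 days | 12% | 2× | 62.3 / 63.0 | 23.0 / 24.7 |
| 84 days | 36% | 2× | 59.9 / 62.1 | 19.2 / 24.7 |
| 84 days | 35% | 4× | 57.5 / 62.9 | 16.0 / 25.0 |
| 168 days | 11% | 2× | 78.8 / 79.0 | 48.5 / 49.5 |
| 168 days | 33% | 4× | 76.8 / 79.1 | 42.2 / 49.8 |

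At 2× to 4× the overstatement at 6 months runs from 49.5 − 48.5 = 1.0 to 25.0 − 16.0 = 9.0 points. At 3 months it runs from about 0 to 62.9 − 57.5 = 5.4 points. At 1× there is no material difference. The estimated median, which sits on a scan day (113 or 169), was the same under both methods in every scenario.

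**The case against.** The best defense is that the Protocol does ask for progression to be documented. Sections 9.1.13 and 14 tie scans to disease progression rather than to the last dose. Section 12.2 wants PD documented before other anti-cancer treatment starts. Appendix A asks for every effort to document objective progression after discontinuation in subjects with symptomatic deterioration. This stands as evidence of intent, so the fair description is conflicting instructions rather than silence. It does not supply a visit, a form item or a date field. The Appendix A note covers only one group, and Section 12.2 itself sends subjects who need other treatment to telephone follow-up.

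Several stronger readings are tempting but not supported:

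- *These subjects are censored at an old scan.* Neither document has a censoring rule. Under the Appendix A definition, a later death learned of by telephone is a PFS event. The inference fits TTP and the CNS non-progression rates better.
- *Practically every end-of-treatment scan is waived.* This is right for brain MRI and for stops from Cycle 3 Day 1 on. It is not right for body scans before that visit if the waiver is read by compartment.
- *The Cycle 2 Day 1 MRI waives the body scan.* This is one reading of the footnotes. Section 9.2.10 more naturally refers to the full assessment.
- *The same argument covers LM progression.* In Cohort B, LM progression is defined by symptoms, not MRI, and the symptom assessment at the end-of-treatment visit is not waived. There the scan argument reaches only BM and non-CNS disease.

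It is also true that the affected endpoints are secondary and that the SAP plans no formal testing.

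**Conclusion.** The point holds in a limited form. Progression follow-up is promised without a procedure, and the waiver window equals the scan interval, so most subjects who stop on schedule without PD have no end-of-treatment scan and no later one. Their progression may go unobserved. That can bias CNS TTP, non-CNS TTP, the 3- and 6-month CNS non-progression rates and, to a lesser degree, PFS, provided that stopping is related to prognosis.

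The size cannot be fixed from the documents. The range of about 1 to 9 points at 6 months rests on assumed stopping rates and a 2- to 4-fold hazard after stopping, with no deaths modeled; with no rise in hazard the bias is negligible. A reader might infer that median PFS is lengthened, but the simulation does not show this. Nor can a stopping rate be read from the 11 of 41 subjects in the earlier 300 mg study: those were dose reductions, and Section 11.1.2 allows two before discontinuation. Nor does each lost subject shift a rate by 1/20 = 5 points, since a Kaplan-Meier estimate does not count a censored subject as progression-free to the landmark. This argument raises no issue with the primary endpoints.

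**What to change.** 1. **Protocol synopsis, Tables 4-1 and 4-2, Sections 9.2.11, 9.2.12 and 11.1.1.** Reconcile the follow-up statements. For subjects who stop without PD, add progression status, date and compartment (CNS or non-CNS) to the existing 8-weekly contact. Collect dates and results of scans done in routine care until PD, new anti-cancer therapy or death.
2. **Footnotes k and n and Section 9.2.10.** State that the waiver applies separately to brain MRI and to thoracic/abdominal imaging, so that a brain-only Cycle 2 Day 1 MRI does not waive the body scan. The documents give no basis for a particular shorter window, so its length can stay.
3. **SAP Section 2.** State event and censoring rules for PFS, CNS TTP, non-CNS TTP and the CNS non-progression rates, including subjects who stop without PD, and report how many there are by cohort.

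**Cost.** One form item, collection of scan reports, a few end-of-treatment body scans already in the schedule that are no longer waived, and SAP text. PFS and TTP may read slightly shorter.

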QOL	quality of life
QTc(F)	QT interval, corrected
RECIST	Response Evaluation Criteria In Solid Tumors
RTK	receptor tyrosine kinases
SADR	suspected adverse drug reactions; also referred to as SAR
SAE	serious adverse event
SAR	suspected adverse reactions; also referred to as SADR
SOC	system organ class
Src	sarcoma
SSRI	selective serotonin reuptake inhibitor
SUSAR	suspected unexpected serious adverse reaction
TEAE	treatment emergent adverse event
TKI	tyrosine kinase inhibitor
TTP	time to progression
ULN	upper limit of normal
VEGFR2	vascular endothelial growth factor receptor 2

5 BACKGROUND AND RATIONALE

5.1 Tesevatinib

Tesevatinib (formerly known as KD019) is an orally administered tyrosine kinase inhibitor, which has been documented to inhibit multiple molecular drivers of tumor growth, including epidermal growth factor receptor (EGFR), human epidermal growth factor receptor 2 (HER2), Src, and VEGFR2.

Tesevatinib is a highly potent inhibitor of the EGFR activating mutations that, when present, drive the growth of non-small cell lung cancers (NSCLCs). When measured in HCC827 cells, which are human lung cancer cells with an EGFR exon 19 deletion, the IC50 for inhibition of EGFR phosphorylation for tesevatinib (0.6 nM) was very similar to that for erlotinib (0.8 nM). The IC50 for inhibition of proliferation in the same cell line was 3.5 nM for tesevatinib and 4.6 nM for erlotinib. Thus tesevatinib and erlotinib have similar potency in vitro against a cell line with an activating EGFR mutation.

5.1.1 Tesevatinib Nonclinical Toxicology

Tesevatinib nonclinical toxicology has been characterized in multiple species using a variety of dosing regimens. Details are provided in the Investigator's Brochure.

The first of the two single-agent Phase 2 studies in NSCLC (Study XL647-201) enrolled treatment naïve patients with advanced stage NSCLC who were Asian, female, or with minimal or no smoking history.¹⁷ There were 41 subjects enrolled in an intermittent dosing schedule and 14 enrolled in a daily dosing schedule. Subjects in the intermittent cohort received tesevatinib at a dose of 350 mg for 5 days every 2 weeks. Subjects in the daily dosing cohort received tesevatinib administered at a dose of 300 mg daily. Retrospective sequencing of tumor samples identified 14/41 subjects with EGFR mutations. The confirmed partial response (PR) rate in subjects with EGFR mutations was 57% (8/14), and an additional 3 subjects with EGFR mutations had unconfirmed PRs. Response rates were similar in the daily and intermittent tesevatinib schedules. Patients with PRs were those whose tumors had Exon 19 deletions as well as those with the L858R mutation. One subject in this study who is on the intermittent schedule has had a long-term response lasting nearly five years and is still receiving tesevatinib therapy.

In the second single-agent tesevatinib study in NSCLC (Study XL647-203), tesevatinib was administered daily at a dose of 300 mg/day to 41 subjects with NSCLC who had disease progression after treatment with other EGFR inhibitors (erlotinib or gefitinib).¹⁸ The most frequently reported adverse events (AEs) were diarrhea, nausea, cough, dry skin, and electrocardiogram (ECG) QTc prolongation. Two (2) of the 41 subjects experienced QTc(F) > 500 msec confirmed by a central cardiology review. (All subjects in all tesevatinib studies with QTc prolongation have been asymptomatic.) Eleven subjects (11; 28%) required a dose reduction for toxicity, most commonly for diarrhea (27%) and rash (18%). Whether EGFR-

related diarrhea or rash were treated aggressively is not clear. There were 12 subjects with documented T790M EGFR mutations, none of whom had a response to tesevatinib treatment.

5.1.2.3 Phase 3

The Phase 3 study (KD019-301) was a double-blind, randomized, and controlled trial of KD019 vs erlotinib in subjects with Stage IIIB/IV non-small cell lung cancer who had progressed after first- or second-line chemotherapy. The study was closed early due to slow enrollment after 8 subjects were entered. One subject who carried an EGFR activating mutation had a partial response to tesevatinib for eight cycles before progressing.

